7.11.3 Vital Signs

Vital sign MAVs, identified by the criteria defined in [Appendix B](#), will be tabulated. If a subject has a MAV for a particular vital signs parameter, all visits for that subject for that parameter will be listed. The number and percentage of subjects with at least 1 post-dose markedly abnormal vital signs measurement will be summarized. The mapping of the subjects who meet the MAV criteria will be listed as a table. All observations, including ones at unscheduled visits, will be included in the MAV evaluation and summaries if MAV criteria are satisfied.

All vital signs will be listed in a data listing.

7.11.4 12-Lead ECGs

ECG MAVs, identified by the criteria defined in [Appendix C](#), will be tabulated. If a subject has a MAV for a particular 12-lead ECG parameter, all visits for that subject for that parameter will be listed. The number and percentage of subjects with at least 1 post-dose markedly abnormal 12-lead ECG measurement will be summarized. The mapping of the subjects who meet the MAV criteria will be listed as a table. All observations, including ones at unscheduled visits, will be included in the MAV evaluation and summaries.

Overall ECG interpretation category (normal, abnormal not clinically significant, abnormal clinically significant, not evaluable) is collected by eCRF at baseline and at each scheduled post-baseline visit. Shifts in ECG interpretation will be presented as cross-tabulations (baseline versus each post-baseline visit) of numbers of subjects with normal, abnormal not clinically significant, and abnormal clinically significant interpretations, not evaluable, with missing, if applicable, and total categories overall.

All ECG parameters will be listed in a data listing.

7.12 Interim Analysis

There is no interim analysis.

7.13 Changes in the Statistical Analysis Plan

Only analysis on Cohort A and B, and Double-Blind treatment period of the study will be presented because study has been terminated early.

Due to the fact that the study was terminated before the finalization of this statistical analysis plan, no summaries nor analysis will be performed for the exploratory endpoints. Data collected on eCRF or from study procedures that are related to the exploratory endpoints will be listed if appropriate. Additionally, no PK parameters will be derived due to early termination of the study.

Appendix A Criteria for Identification of Markedly Abnormal Laboratory Values
Hematology – Criteria for Markedly Abnormal Values (SI units)

Parameter	Unit	Low Abnormal	High Abnormal
Hemoglobin	Both	$< 0.8 \times \text{LLN}$	$> 1.2 \times \text{ULN}$
Hematocrit	Both	$< 0.8 \times \text{LLN}$	$> 1.2 \times \text{ULN}$
RBC count	Both	$< 0.8 \times \text{LLN}$	$> 1.2 \times \text{ULN}$
WBC count	Both	$< 0.5 \times \text{LLN}$	$> 1.5 \times \text{ULN}$
Platelet count	Conventional	$< 75 \times 10^3/\mu\text{L}$	$> 600 \times 10^3/\mu\text{L}$
	SI	$< 75 \times 10^9/\text{L}$	$> 600 \times 10^9/\text{L}$
Reticulocytes	Conventional	--	$> 3\%$ of erythrocytes
	SI	--	> 0.030 Fraction of 1

LLN=lower limit of normal, RBC=red blood cell, ULN=upper limit of normal, WBC=white blood cell.

Serum Chemistry – Criteria for Markedly Abnormal Values (SI units)

Parameter	Unit	Low Abnormal	High Abnormal
ALT	Both	--	>3 × ULN
AST	Both	--	>3 × ULN
GGT	Both	--	>3 × ULN
Alkaline phosphatase	Both	--	>3 × ULN
Calcium	Conventional	<7.0 mg/dL	>11.5 mg/dL
	SI	<1.75 mmol/L	>2.88 mmol/L
Chloride	Conventional	<75 mEq/L	>126 mEq/L
	SI	<75 mmol/L	>126 mmol/L
Total bilirubin	Conventional	--	>2.0 mg/dL
	SI	--	>34.2 µmol/L
Albumin	Conventional	<2.5 g/dL	--
	SI	<25 g/L	--
Total protein	Both	<0.8 × LLN	>1.2 × ULN
Creatinine	Conventional	--	>2.0 mg/dL
	SI	--	>177 µmol/L
Blood urea nitrogen	Conventional	--	>30 mg/dL
	SI	--	>10.7 mmol/L
Sodium	Conventional	<130 mEq/L	>150 mEq/L
	SI	<130 mmol/L	>150 mmol/L
Potassium	Conventional	<3.0 mEq/L	>6.0 mEq/L
	SI	<3.0 mmol/L	>6.0 mmol/L
Glucose	Conventional	< 50 mg/dL	>350 mg/dL
	SI	< 2.8 mmol/L	>19.4 mmol/L
Bicarbonate	Conventional	<8.0 mEq/L	--
	SI	<8.0 mmol/L	--
Creatine kinase	Conventional	--	>5 × ULN
	SI	--	>5 × ULN
Total Cholesterol	Conventional	--	>300 mg/dL
	SI	--	>7.72 mmol/L
Triglycerides	Both	--	>2.5 × ULN
LDL Cholesterol	Conventional	< 50 mg/dL	>160 mg/dL
	SI	<1.30 mmol/L	>4.14 mmol/L
HDL Cholesterol	Conventional	<40 mg/DL	>60mg/DL
	SI	<1.04 mmol/L	>1.55 mmol/L
Direct Bilirubin	Conventional	--	>2 x ULN
Phosphorus	Conventional	<1.6mg/dL	>6.2 mg/dL
	SI	<0.52 mmol/L	>2mmol/L

ALT=alanine aminotransferase, AST=aspartate aminotransferase, GGT=γ-glutamyl transferase, LLN=lower limit of normal, ULN=upper limit of normal.

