7.11 Safety Analysis

Safety measures include AEs, clinical laboratory parameters, vital sign parameters, 12-lead ECG results, and other safety parameters. The safety analysis set will be used for all summaries of safety parameters.

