7.11.2 Clinical Laboratory Evaluations

Clinical laboratory tests will be assessed using the safety analysis set and will be evaluated and presented using International System of Units (SI) unless otherwise stated. [Table 7.a](#) shows a list of all clinical laboratory tests.

Table 7.a Clinical Laboratory Tests

Hematology	Serum Chemistry	Urinalysis	Special
Red blood cells	Alanine aminotransferase	To be done at local laboratory	To be done at local laboratory
Reticulocytes	Alkaline phosphatase		
White blood cells with differential	Aspartate aminotransferase	pH	Coomb's test
Hemoglobin	γ-Glutamyl transferase	Specific gravity	Platelets, red blood cells, white blood cells with differential
Hematocrit	Total bilirubin	Protein	
Platelets	Direct bilirubin	Glucose	
	Albumin	Blood	To be done at central laboratory
	Total protein	Nitrite	
	Creatinine	Microscopic Analysis:	Lipid panel (fasted):
	Blood urea nitrogen	RBC/high power field	Total cholesterol
	Creatine kinase	WBC/high power field	LDL-cholesterol
	Potassium	Epithelial cells, casts, etc	HDL-cholesterol
	Sodium		Triglycerides
	Glucose	To be done at central laboratory	Serum complement
	Chloride	Urine protein and creatinine for UPCR	C3 and C4
	Phosphorus	Urine Biomarkers	Total IgM, IgG and IgA
	Calcium	To be done at the site	Autoantibodies:
		Standard urinalysis using dipstick (protein only)	Anti-double-stranded DNA
			Anti-nuclear antibody
			Anti-Ro (SS-A)
			Anti-La (SS-B)
			Anti-RNP
			Anti-Sm
			Anti-phospholipids
			Serum biomarkers
			Tetanus antibody titers
			HBsAb titers

Serum

Serum hCG (a)

At Screening Only:

Hepatitis panel, including HBsAg, anti-HCV and HIV

FSH (b)

DNA=deoxyribonucleic acid, FSH=follicle-stimulating hormone, HBsAb=hepatitis B surface antibody, hCG=human chorionic gonadotropin, HDL=high-density lipoprotein, HIV=human immunodeficiency virus, LDL=low-density lipoprotein.

(a) Serum hCG pregnancy test will be done on all female subjects of childbearing potential at Screening.

(b) The FSH level will be obtained for female subjects at Screening if they are postmenopausal by history (ie, last regular menstrual cycle >2 years) and not surgically sterile. The FSH result must be >40 IU/L for the subject to be permitted not to use adequate contraception.

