All laboratory test parameters will be displayed in individual subject data listings in both SI units and conventional (CV) units. For test results not in SI units, the conversion to SI units will be done in derived analysis data sets using the known conversion factors. If necessary, SI units from the central laboratory may be converted to Takeda's preferred SI units in the derived dataset. All summaries and analyses will be based on the values using these preferred SI units.

Descriptive statistics (N, mean, SD, median, minimum, and maximum) for the observed baseline, post-baseline and change from baseline values will be presented by pooled placebo group, ixazomib doses, and ixazomib overall for the following laboratory tests:

- Red blood cells.
- White blood cells with differential.
- Platelets.
- Alanine aminotransferase.
- Alkaline phosphatase.
- Aspartate aminotransferase.
- γ -Glutamyl transferase.
- Total bilirubin.
- Creatinine.
- Blood urine nitrogen.
- Urine protein and creatinine for UPCR.
- C3 and C4.
- Total IgM, IgG and IgA.
- Anti-double-stranded DNA.
- Tetanus antibody titers.
- HBsAb titers.

Study baseline will be used for change from baseline.

Laboratory Markedly Abnormal Values (MAVs), identified by the criteria defined in [Appendix A](#), will be tabulated. If a subject has a MAV for a particular laboratory test, all visits for that subject for that parameter will be listed. The number and percentage of subjects with at least 1 post-dose markedly abnormal laboratory test result will be summarized. The mapping of the subjects who meet the MAV criteria will be listed as a table. All observations, including ones at unscheduled visits, will be included in the MAV evaluation and summaries if MAV criteria are satisfied.

All clinical laboratory data will be presented in both SI and conventional units in data listings.

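### Appendix A labels HDL cholesterol outside 40 to 60 mg/dL as markedly abnormal, so ordinary HDL values would fill the general (non-primary) laboratory MAV displays

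*SAP*

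**What the plan says.** Appendix A of the SAP is titled "Criteria for Identification of Markedly Abnormal Laboratory Values". Its serum chemistry table gives HDL a low and a high limit, "HDL Cholesterol Conventional <40 mg/DL >60mg/DL", and repeats them in SI units as "<1.04 mmol/L >1.55 mmol/L". The other lipid rows are built differently:

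- Total cholesterol has a high limit only: "Total Cholesterol Conventional -- >300 mg/dL".
- Triglycerides have a high limit only, at 2.5 times the upper limit of normal.
- LDL is two-sided, with flags below 50 and above 160 mg/dL.

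HDL is measured in this trial as part of the fasted lipid panel in Table 7.a. Section 7.11.2 applies Appendix A to the laboratory data and states: "The number and percentage of subjects with at least 1 post-dose markedly abnormal laboratory test result will be summarized". It also states: "All observations, including ones at unscheduled visits, will be included in the MAV evaluation and summaries if MAV criteria are satisfied". Flagged subjects are mapped in a table, and all their visits for the flagged test are listed. No sentence exempts HDL or explains its limits.

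**The concern.** A markedly abnormal flag is useful when it picks out results that stand clear of everyday variation. The HDL row leaves a window of only 20 mg/dL unflagged, on a test whose values may well spread more widely than that between subjects. The rule also has no baseline condition: a subject who enters the trial at 65 mg/dL and stays there counts as having a post-dose MAV. The SAP can write a baseline condition when it wants one, since part of the QTc criterion in Appendix C requires a change from baseline.

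At stake is the general laboratory MAV display in a trial whose primary objective is safety and tolerability. Section 7.11.2 includes no lipid test in its list for descriptive statistics, so the MAV tabulation is the only HDL summary that it specifies. If that tabulation is driven by where subjects started, it says little about the drug.

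**Working it through.** **Inputs from the SAP**

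- HDL limits of 40 and 60 mg/dL (1.04 and 1.55 mmol/L), and the comparison rows: Appendix A.
- The counting rule: section 7.11.2.
- Planned size of at least 4 active and 1 placebo subject in each of Cohorts A and B: section 6.0. Only these two cohorts are presented (section 7.13), and placebo is pooled (section 7.1).

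**Assumptions not in the SAP**

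- A cholesterol conversion factor of 38.67 mg/dL per mmol/L.
- Normally distributed HDL with mean μ from 45 to 60 and SD σ from 10 to 18 mg/dL, and one post-dose reading per subject.

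**Step 1: are the limits a unit slip?** 40 / 38.67 = 1.034 and 60 / 38.67 = 1.552. The stated 1.04 and 1.55 agree to within 0.01 mmol/L, so both rows express the same limits.

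**Step 2: how narrow is the band?** For HDL, 60 − 40 = 20 mg/dL and 60 / 40 = 1.5. For LDL, 160 − 50 = 110 mg/dL and 160 / 50 = 3.2. High-to-low ratios for other rows with two fixed limits are:

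- platelets 600 / 75 = 8.0
- glucose 350 / 50 = 7.0
- phosphorus 6.2 / 1.6 = 3.9
- potassium 6.0 / 3.0 = 2.0
- chloride 126 / 75 = 1.68
- calcium 11.5 / 7.0 = 1.64
- sodium 150 / 130 = 1.15

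HDL is the tightest except for sodium. The ratio is only descriptive, because it ignores how much each test varies between people.

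**Step 3: share of subjects flagged on one reading.** p = Φ((40 − μ)/σ) + 1 − Φ((60 − μ)/σ).

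| μ | σ | Below 40 | Above 60 | p |
|---|---|---|---|---|
| 50 | 10 | 0.159 | 0.159 | 0.317 |
| 45 | 10 | 0.309 | 0.067 | 0.375 |
| 50 | 15 | 0.252 | 0.252 | 0.505 |
| 55 | 15 | 0.159 | 0.369 | 0.528 |
| 60 | 18 | 0.133 | 0.500 | 0.633 |

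Over the whole grid p runs from 0.317 to 0.633, or about 32% to 63%. With the upper limit removed and the lower one kept, only the low tail remains: 0.023 (μ = 60, σ = 10) to 0.391 (μ = 45, σ = 18), or about 2% to 39%.

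**Step 4: effect on the reported percentage.** Section 7.11.2 does not say whether the percentage is per test or across tests.

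- *Per test:* the HDL row shows about 32% to 63%, and no other row changes.
- *Across tests:* suppose, for illustration, that 30% of subjects have a MAV on some other test, independently of HDL. The pooled figure is 1 − 0.70 × (1 − p). With p = 0.317 this is 1 − 0.70 × 0.683 = 0.52; with p = 0.633 it is 1 − 0.70 × 0.367 = 0.74. So 30% becomes 52% to 74%.

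**Step 5: small groups.** At the planned minimum, one flagged subject moves a dose group by 1/4 = 25 percentage points and pooled placebo by 1/2 = 50 points. The chance that at least one of 4 active subjects is flagged on HDL is 1 − (1 − p)^4, which is 0.78 to 0.98 over the grid. That is the chance of seeing any flag in the group; it is not the percentage that the SAP reports.

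**The case against.** The strongest reply is that little depends on this row. MAVs are not adverse events, the study is not powered for any test, and a reader can use the mapping and listings to see which flags come from HDL alone. The wording around the summary in section 7.11.2 refers to a particular test and parameter, which favours per-test reporting; in that case no row other than HDL's is disturbed. Two-sided fixed limits are not unique to HDL among the lipids, since LDL has them too, and sodium has a tighter band. The SAP gives no HDL reference range or distribution, and no view on whether a high value matters for safety. All of this stands, and it limits the weight of the point.

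A reader might infer three stronger things that the SAP does not support:

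- **That a primary endpoint is inflated.** Section 5.1.1 restricts the primary MAV endpoint to hematologic parameters, and HDL is in the serum chemistry table.
- **That the MAV percentage is driven towards 100% in every group.** The single-reading share is 32% to 63% under the assumptions, and the pooled illustration reaches 74% at most. The 78% to 98% in step 5 measures something else. Repeat readings can only raise a subject's chance of being flagged, but by how much cannot be said: the SAP gives neither the number of post-dose lipid samples nor the within-subject correlation.
- **That every flagged value is favourable.** That could apply at most to the high side, and it is general clinical knowledge, not something in the SAP. A value below 40 mg/dL is low; the question there is whether it is marked.

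**Conclusion.** The point holds, as a minor one. The HDL limits are internally consistent but far tighter than the other lipid rows, and section 7.11.2 sends every post-dose hit into the MAV tabulation, mapping and listing without regard to baseline. The criterion therefore does not do what the title of Appendix A says.

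Under the assumed distributions, about 32% to 63% of subjects would be flagged on a single HDL reading. This inflates the any-test percentage only if that percentage is pooled across tests; reported per test, the HDL row alone becomes uninformative. The narrow band and the counting rule are read directly from the SAP. The size depends entirely on the assumed means and SDs, which nothing in the SAP ties to this lupus nephritis population.

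**What to change.** In Appendix A, replace the HDL upper limit with '--' in both unit rows. This presumes that the sponsor has no safety reason to flag high HDL; the SAP records none. Removing the upper limit alone may still leave up to 39% of subjects flagged under the assumptions above, so also do one of the following:

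- have the sponsor reset the lower limit to one that identifies a marked abnormality; or
- take HDL out of the MAV count and keep it in the listings.

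Stating in section 7.11.2 whether the percentage is per test or across tests would settle how far the row matters.

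The cost is one table row and one programming parameter, with no new data. The downside is that a mildly low HDL would appear only in the listing. If HDL leaves the MAV count altogether, the same holds for every HDL value, because section 7.11.2 specifies no other HDL summary.

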Appendix B Criteria for Markedly Abnormal Vital Signs

Parameter	Unit	Lower Criteria	Upper Criteria
Pulse	bpm	<50	>120
Systolic blood pressure	mm Hg	<85	>180
Diastolic blood pressure	mm Hg	<50	>110
Body temperature	°C	< 35.6	>37.7

Appendix C Criteria for Markedly Abnormal 12-Lead ECG Parameters

Parameter	Unit	Lower Criteria	Upper Criteria
Heart Rate	bpm	< 50	> 120
PR	msec	≤ 80	≥ 200
RR	msec	≤ 600	≥ 1440
QRS	msec	≤ 80	≥ 180
QT Interval	msec	≤ 50	≥ 460
QTcB Interval	msec	≤ 50	≥ 500 OR ≥ 30 change from baseline and ≥ 450
QTcF Interval	msec	≤ 50	≥ 500 OR ≥ 30 change from baseline and ≥ 450

ELECTRONIC SIGNATURES

Signed by	Meaning of Signature	Server Date (dd-MMM-yyyy HH:mm 'UTC')
Personal Protected Information	Biostatistics Approval	07-Mar-2018 18:01 UTC
	Pharmacovigilance Approval	07-Mar-2018 18:27 UTC
	Clinical Approval	07-Mar-2018 18:35 UTC
	Clinical Pharmacology Approval	07-Mar-2018 19:39 UTC
	Biostatistics Approval	08-Mar-2018 15:02 UTC

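### In SAP Appendix C the RR limits (equal to ≥100 or ≤41.7 bpm) contradict the heart-rate limits (>120 or <50 bpm), so one tracing can be markedly abnormal by one row and not by the other

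*SAP*

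**What the plan says.** Appendix C of the SAP lists the criteria for markedly abnormal 12-lead ECG parameters. Two of its rows concern ventricular rate:

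- Heart rate: "Heart Rate bpm < 50 > 120"
- RR interval: "RR msec ≤ 600 ≥ 1440"

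Appendix B, for vital signs, has a third row on the same quantity: "Pulse bpm <50 >120".

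Section 7.11.4 (12-Lead ECGs) takes its MAV definitions from Appendix C and builds several outputs on them:

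- A count and percentage: "The number and percentage of subjects with at least 1 post-dose markedly abnormal 12-lead ECG measurement will be summarized".
- A listing by parameter: "If a subject has a MAV for a particular 12-lead ECG parameter, all visits for that subject for that parameter will be listed".
- A subject mapping: "The mapping of the subjects who meet the MAV criteria will be listed as a table".

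Section 7.11.3 does the same for vital signs from Appendix B: "The number and percentage of subjects with at least 1 post-dose markedly abnormal vital signs measurement will be summarized".

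The SAP gives no reason for the heart-rate and RR limits to differ, and no rule for a tracing on which the two rows disagree.

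**The concern.** Heart rate and RR interval are one quantity on two scales, and each determines the other. Two sets of limits on them should describe the same rates unless the plan says why not. Here they do not, and the difference changes direction: the RR row flags more tracings at the fast end and fewer at the slow end.

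Appendix C feeds the ECG MAV tables directly, so this would show in the report. The heart-rate and RR lines could give different counts from the same tracings. A rate of 100 to 120 bpm would be flagged on the ECG through RR, while the heart-rate row and the pulse row behind the vital-sign summary would both leave it unflagged. A reader could not tell whether such a difference is a finding in the subjects or a product of the limits.

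**Working it through.** **Inputs.** Heart-rate limits <50 and >120 bpm, and RR limits ≤600 and ≥1440 msec (both Appendix C). Pulse limits <50 and >120 bpm (Appendix B).

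**Formula.** RR (msec) = 60,000 / rate (bpm), and the reverse. This assumes that both values come from the same tracing and that the reported rate corresponds to the mean RR.

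**Step 1: put both rows on both scales.**

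| Row | Fast limit | Slow limit |
|---|---|---|
| Heart rate, as written | >120 bpm | <50 bpm |
| Heart rate, as RR | <60,000/120 = 500 msec | >60,000/50 = 1200 msec |
| RR, as written | ≤600 msec | ≥1440 msec |
| RR, as heart rate | ≥60,000/600 = 100 bpm | ≤60,000/1440 = 41.7 bpm |

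**Step 2: size of the gaps.** Fast end: 120 − 100 = 20 bpm. Slow end: 50 − 41.7 = 8.3 bpm.

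**Step 3: is it rounding?** The RR limits divided by the RR equivalents of the heart-rate limits are 600/500 = 1.2 and 1440/1200 = 1.2. Both are off by the same factor, so the shift is systematic. Rounding or a different averaging of beats would move an edge by about 1 bpm at most.

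**Step 4: where the rows disagree.**

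| Rate (bpm) | RR (msec) | By heart rate | By RR |
|---|---|---|---|
| ≤41.7 | ≥1440 | MAV | MAV |
| above 41.7, below 50 | above 1200, below 1440 | MAV | not MAV |
| 50 to below 100 | above 600, up to 1200 | not MAV | not MAV |
| 100 to 120 | 500 to 600 | not MAV | MAV |
| >120 | <500 | MAV | MAV |

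The slow edge can be checked on whole numbers. At 42 bpm RR is 60,000/42 = 1428.6 msec, not flagged by RR. At 41 bpm it is 60,000/41 = 1463.4 msec, flagged.

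**Step 5: count of discordant whole-number rates.** 100 to 120 bpm gives 21 values and 42 to 49 bpm gives 8, so 21 + 8 = 29. Of the 71 whole-number rates from 50 to 120 bpm that the heart-rate row leaves unflagged, the RR row flags 21. These figures show the width of the conflict, not how often it would occur, because the SAP gives no heart-rate distribution.

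**Step 6: effect on the subject count.** Section 7.11.4 does not say whether the count of subjects with at least 1 MAV is taken per parameter or across parameters.

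- Per parameter: the heart-rate and RR lines can differ at both ends.
- Across parameters: a tracing at 100 to 120 bpm enters through RR. The slow-end conflict does not change the total, because the heart-rate row already flags those tracings.

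**Step 7: what one subject is worth.** Section 7.13 limits reporting to Cohorts A and B, and section 6.0 plans at least 4 active and 1 placebo subjects in each. If exactly these minimums were treated (an assumption, since actual numbers are not given), one subject flagged by only one row moves a dose group by 1/4 = 25 percentage points and ixazomib overall by 1/8 = 12.5 points.

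**The case against.** The best case on the other side concerns weight.

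- **Separate parameters.** Heart rate and RR are separate rows, each can be programmed as written, and no analysis step requires them to agree. That is so, but the plan still puts two different thresholds on one quantity without a reason. A more sensitive RR screen cannot be the reason, since the RR row is looser at the slow end.
- **Small consequence.** ECGs are an additional safety assessment (section 5.1.4). The only primary endpoint built on MAVs is hematologic (section 5.1.1). The study was terminated early, only Cohorts A and B are presented, and the summaries are descriptive. All of this stands.
- **Other views of the data.** Section 7.11.4 also cross-tabulates the overall ECG interpretation, baseline against each post-baseline visit, without using Appendix C. It adds: "All ECG parameters will be listed in a data listing". With so few subjects, a reader can inspect each value. This limits the harm but does not make the MAV tables consistent.
- **Counting whole-number rates says nothing about frequency.** Correct. The threshold gaps of 20 and 8.3 bpm are the firm measure of size.

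The objection limits the importance of the point and leaves the contradiction in place.

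**Conclusion.** The concern holds. Appendix C contradicts itself: as written, tracings at 100 to 120 bpm are MAVs by RR only, and tracings above 41.7 and below 50 bpm are MAVs by heart rate only. The conclusion rests on the SAP's own limits and the reciprocal relation between rate and RR, with both taken from the same tracing. The ratio of 1.2 shows that the gap is not rounding. It does not show which row departs from what was intended, or why. Agreement of Appendix B's pulse row with the heart-rate row makes RR the odd one out but does not settle the matter.

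This should be corrected because it feeds reported tables directly and costs little. It does not threaten the primary safety results, and the number of subjects affected may be zero.

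**What to change.** Reconcile the heart-rate and RR rows of Appendix C so that they express the same rates, or keep only one as the rate criterion. The sponsor must decide which row was intended. The arithmetic equivalents are:

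- If the heart-rate row was intended, RR becomes <500 or >1200 msec.
- If the RR row was intended, heart rate becomes ≥100 or ≤41.7 bpm, and the pulse row of Appendix B must be checked as well.

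The cost is a correction to one row of Appendix C and a rerun of the ECG MAV outputs if they have been produced. If the pulse row also changes, the vital-sign MAV outputs need a rerun. No data or design change is involved.

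A minor query, separate from the point above: the lower limits for QT, QTcB and QTcF in Appendix C (≤50 msec) lie below the lower limit for QRS (≤80 msec) and look implausible for valid recordings. Those three entries should be checked against their source at the same time.

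### The QRS lower criterion (80 msec or less, with no baseline condition) counts subjects with a stable, ordinary narrow QRS as having a markedly abnormal ECG

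*SAP*

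**What the plan says.** SAP Appendix C sets the QRS limits as "QRS msec ≤ 80 ≥ 180", that is, a low flag at 80 msec or less and a high flag at 180 msec or more. Neither depends on the subject's baseline value.

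Section 7.11.4 applies the table directly: it opens with "ECG MAVs, identified by the criteria defined in" and a reference to this appendix, and it lists every visit of a flagged subject for the parameter concerned. The summary rule is "The number and percentage of subjects with at least 1 post-dose markedly abnormal 12-lead ECG measurement will be summarized". On which tracings count, it says "All observations, including ones at unscheduled visits, will be included in the MAV evaluation and summaries".

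Two other rows of Appendix C are useful for comparison. PR has "PR msec ≤ 80 ≥ 200", with the same lower figure as QRS. QTcB and QTcF have the upper criterion "≥ 500 OR ≥ 30 change from baseline and ≥ 450", so the second arm of that criterion does use change from baseline.

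Outside the MAV count, Section 7.11.4 plans one more ECG table, "Shifts in ECG interpretation will be presented as cross-tabulations (baseline versus each post-baseline visit"), and a listing of all ECG parameters. It plans no descriptive statistics for ECG intervals.

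**The concern.** A criterion labelled markedly abnormal should not be met by ordinary tracings. If the usual adult QRS range is about 70 to 110 msec, the low flag takes in the bottom 10 msec of that range. Because there is no baseline condition and a single post-dose ECG is enough, a subject whose QRS never changes can enter the count purely through having a narrow QRS.

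The groups are very small, so this matters more than it would in a larger study. Section 7.13 restricts reporting to Cohorts A and B, and Section 6.0 plans at least 4 active and 1 placebo subjects in each. One flag moves a dose group of 4 by 25 percentage points. In a study whose primary objective is safety and tolerability, a reader of the summary table could take such a figure for a drug or dose effect.

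**Working it through.** The SAP gives no figure to reproduce here. The check has two parts: what the text does to individual subjects, and how often it would flag subjects whom the drug has not affected.

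**Rule applied to individual subjects**

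- QRS steady at 80 msec, baseline and post-dose: meets the low criterion and is counted.
- QRS from 90 to 150 msec (+60): meets neither criterion and is not counted.
- QTcF steady at 460 msec: below 500 and no change of 30 or more, so it is not counted. A stable QTcF in this range is protected by the change condition, whereas a stable QRS is not.

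**Frequency of flags without a drug effect**

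Inputs from the SAP: cut-off of 80 msec or less (Appendix C), any post-dose ECG (7.11.4), planned minimum of 4 active subjects per cohort and so 8 in Cohorts A and B together (6.0, 7.13).

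Assumed inputs, because the SAP has no QRS data: normal distribution, mean 85 to 100 msec, SD 8 to 12 msec, whole-msec readings (hence a cut at 80.5), one ECG per subject, independent subjects.

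Formulas: p = Φ((80.5 − mean)/SD), and P(at least 1 of n) = 1 − (1 − p)^n.

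Worked case, mean 90 and SD 10:

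- p = Φ((80.5 − 90)/10) = Φ(−0.95) = 0.171
- n = 4: 1 − 0.829^4 = 0.528, or 53%
- n = 8: 1 − 0.829^8 = 0.777, or 78%
- expected number flagged among 8: 8 × 0.171 = 1.37

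All cases, shown as p and then the chance of at least 1 of 4:

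| Mean (msec) | SD 8 | SD 10 | SD 12 |
|---|---|---|---|
| 85 | 0.287; 74% | 0.326; 79% | 0.354; 83% |
| 90 | 0.118; 39% | 0.171; 53% | 0.214; 62% |
| 95 | 0.035; 13% | 0.074; 26% | 0.113; 38% |
| 100 | 0.007; 3% | 0.026; 10% | 0.052; 19% |

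For 8 subjects the range is 6% to 97%, with 0.06 to 2.8 subjects expected to be flagged. These are single-ECG figures. Because one qualifying tracing is enough and unscheduled ECGs are included, repeat ECGs can only raise them.

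Weight of one flag: 1/4 = 25% of a dose group of 4, and 1/2 = 50% of a pooled placebo group of 2 (1 per cohort).

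The high criterion is practically never met by an unaffected subject: the chance of 180 msec or more is below 1e-10 in every case above. Under these assumptions, QRS flags in unaffected subjects come only from the low side.

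**The case against.** The strongest reply is that the effect is small and visible. ECG MAVs are descriptive, the only MAV-based primary endpoint in Section 5.1.1 is hematologic, and the study tests no hypothesis. The same criterion applies to placebo, so false flags add noise and do not favour one arm in expectation. Section 7.11.4 also lists all visits for a flagged parameter and maps the subjects concerned, so with so few subjects a steady QRS of 80 could be traced. All of this stands and it limits the severity. It does not make the summary percentage meaningful.

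It is also fair that the size depends on assumptions. At mean 100 and SD 8 the chance for 4 subjects is only about 3%, and 4 is a planned minimum in a study that stopped early. Nor would changing the QRS row clean up the whole ECG MAV count. The RR row flags 600 msec or less, which is 60,000/600 = 100 bpm or more, while the heart rate row flags only above 120 bpm.

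Three stronger readings are tempting, and the SAP does not support them.

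- A reader might infer that the table misses conduction slowing. It flags PR of 200 msec or more, and QRS of 180 msec or more. What falls outside the MAV count is QRS widening that stays below 180 msec.
- A reader might infer that such widening would appear in no table. If the ECG reader judges it abnormal, it can show in the interpretation shift tables, and the values are listed in any case.
- A reader might infer that 180 msec is an error, or that the lower 80 was carried over from the PR row. Nothing in the SAP contradicts 180 as a limit for marked abnormality, and the shared figure proves no copying.

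**Conclusion.** The point holds for the lower QRS criterion. As written, Appendix C and Section 7.11.4 together count a subject with a stable QRS of 80 msec or less as having a markedly abnormal ECG. That these are ordinary tracings rests on the assumed adult range of about 70 to 110 msec. The conclusion needs only that the lower end of the usual range lies below 80 msec.

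The frequency is uncertain: about 3% to 83% for at least 1 flag among 4 unaffected subjects on one ECG, 53% in the middle case. The consequence for a dose group of 4 is not uncertain, since each flagged subject adds 25 percentage points.

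The upper limit is a query and not a finding. Severity is minor: no estimate of a primary endpoint and no decision rule in the SAP depends on this row.

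**What to change.** In the QRS row of Appendix C, do one of the following:

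- delete the lower criterion; or
- count it only when it was not met at baseline and QRS has changed from baseline by an amount written into the row, in the way the second arm of the QTc criterion requires a change.

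Keep every QRS value in the ECG listing, so that no data are lost. Because the study had already been terminated when the SAP was finalised, record the date of the change and whether treatment codes had been broken. If the tables already exist, a footnote and a second count without the QRS lower criterion would serve.

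Separately, ask the sponsor to confirm that 180 msec is the intended upper limit, given that widening below it does not enter the MAV count.

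The cost is one appendix row and the matching line of table programming. The downside is that, if Appendix C is the sponsor's standard MAV table, this row will differ from other studies that use it.
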